# C.5. Aim 2: Test a set of automated reminders (defined during Aim 1) on timely receipt of next needed HPV vaccine dose and on series completion.

We hypothesize that Auto and Auto-Plus interventions will be more effective than usual care, and Auto-Plus will be more effective than Auto at increasing receipt of the next needed HPV vaccine dose and on series completion. We will implement and evaluate the intervention in 4 clinics using an individual-RCT design (IM Steps 5 and 6). Our quantitative evaluation will assess intervention effectiveness and reach. We will gather P/C-, patient- and HCP-level data to identify possible program enhancements, as well as barriers and facilitators to adoption, implementation, and maintenance.

**C.5.a.** Convene Teams and Train Staff: Each participating clinic will convene an implementation team comprised of a clinic champion, clinic coordinator, and relevant laboratory and administrative personnel whom we will select for their ability to facilitate the intervention within the clinic settings. Once the team is formed, members of the PREVENT research team and clinic staff will train the participating clinics in delivering the intervention. Staff training will take place during a half-day session (with additional phone support) and will address procedures for identifying P/C of eligible patients and tracking automated outreach (e.g., automated phone calls, text messages). Clinics will receive training specific to the Auto-Plus components, such as the live phone call and patient navigation protocols using as computer assisted interactive system.

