C.5.b. Intervention Process: Focused on HPV vaccine initiation. Through BCT, we will select a set of HPV vaccine initiation reminders to encourage uptake among age- and vaccine-eligible adolescents. Reminders could include letters (with strong provider recommendations, and bundled recommendations), text messages with links to digital stories, patient and/or P/C narratives, letters, automated phone calls, or email messages. Because we hope to implement this trial as part of standard care, our study will apply to obtain a waiver of informed consent, which was successful in STOP CRC because intervention components are similar to primary health care settings' standards of care and imply minimal risk (See Section C.2). Sea Mar analysts will create a real-time list of patients due for an initial HPV vaccine dose, and the clinic outreach coordinator will review the list and remove any patients missing telephone number or address (if a mailed intervention is selected). P/C of remaining children and adolescent patients (i.e., participants) will be individually randomized to either Auto or Auto-Plus intervention or UC, in a 1:1:1 ratio. The PREVENT study will only target one child/adolescent per parent/caregiver (siblings will be excluded from intervention assessments). In Sea Mar clinics, 87% of phone numbers of patients eligible for CRC screening (aged 50-75) could receive text messages; we expect a higher percentage for the younger cohort in this trial.88 Participant lists will be sent to Sea Mar's communications vendor (ClienTell) for delivery of automated HPV vaccine initiation prompts; the UC group will not receive tailored reminders but will only receive opportunistic vaccine reminders that are delivered during clinic visits or MyChart EHR-based patient portal reminders. As in STOP CRC, real-time participant lists will be refreshed to discontinue reminders for P/C of patients who have received a given vaccine dose.

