Consistent with the desire of clinic staff to integrate this project into their standard workflows, we will use automated codes to manage interventions so that eligible patients get initial HPV vaccines on time and P/C are prompted to repeat vaccination, as recommended. Our EHR tools rely on Reporting Workbench, a population management tool in Epic which will be customized to include tools needed for tracking completion of HPV vaccination at the 4 intervention clinics. The registry will list patients' HPV vaccination history as well as key demographic variables for the intervention (e.g., name, address, preferred language). We will select a cohort of approximately 1,038 P/C of patients from the 4 clinics, randomized to intervention arms (UC, Auto, and Auto-Plus) stratified by clinic, sex, and language preference (English, Spanish, other) to ensure a nearly balanced distribution of clinic, sex, and language preference among study arms. The registry will generate 2 real-time reports: 1] HPV vaccination outcomes (i.e., date of vaccination events, and whether the event represents series initiation, second dose, and/or series completion); and 2] PREVENT intervention activities (i.e., date of

Table 3: Schedules of Measures (part.=participants; T=time, Y=year; M=month)								
Variable	Data source	How measured	Proctor/ RE- AIM domain	Т				
Aim 1: Bootcamp Translation (BCT)								
Rural parent-/ caregiver- & provider-driven adaptations/ program acceptance	Parents / providers	Notes from BCT sessions	Adaptations, Acceptance	Y 1				
Aim 2: PREVENT Randomized 0	Controlled Trial (I							
Reach of RCT – primary outcome (next needed HPV vaccine dose)	EHR; vendor logs	N part. receive program/ N anticipated, reasons	Reach	6 m				
Reach of RCT – secondary outcome (completion of HPV vaccine series)	EHR; vendor logs	N part. receive program/ N anticipated, reasons	Reach	6 m				
Effectiveness of RCT – primary outcome	EHR	N C/A complete next HPV vaccine dose/ N anticipated	Effectiveness	6 m				
Effectiveness of RCT – secondary outcome	EHR	N C/A complete all doses of HPV vaccine  / N anticipated	Effectiveness	13 m				
Aim 3: Tertiary and Qualitative	Outcomes							
Moderators (e.g., sex of parent, sex of child, age, ethnicity, etc.)	EHR data	Effectiveness of intervention by presence of moderator	Equity	6 m				
Parent/caregiver reactions	Interviews	Coded transcripts	Acceptance	Y 3				

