Program Effectiveness: We will assess intervention effectiveness for each of the three study arms, calculated as the proportion of eligible children/adolescents who received any HPV vaccine within 6 months and 13 months (series completion by one year) of randomization. We will assess the proportion of C/A who initiated HPV vaccination, those who received the next needed dose and the percent who completed the series.

Study Design: We propose a 3-arm RCT to compare rates of completing the next step in the HPV vaccination series at 6 months and completing the HPV vaccination series at 13 months between Auto, Auto-Plus, and UC arms. P/C of C/A who have not completed the HPV vaccination series will be randomized 1:1:1 to study arms, with separate randomizations within each clinic (Ocean Shores, Aberdeen, Elma, or Yelm) and patient-level HPV vaccination initiation status (series initiated or not initiated). Participants will be assessed for eligibility and, if eligible, enrolled within the 4 clinics at their first visit time during the 12-month study period, with a total participant time on study of 13 months, for a total of 25 months of enrollment, execution, and follow-up.

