Statistical Approaches: The primary comparisons are between the rates of completing the next step in the HPV vaccination series at 6 months in the Auto, Auto-Plus, and UC arms (Primary Outcome), and between the rates of completing the HPV vaccination series at 13 months (Secondary Outcome). Completing the next step in the vaccine series and completing the vaccine series outcomes will be compared via logistic generalized estimating equations (GEE) models, 129, 130 with bias-reduced robust sandwich variance estimators 131 clustered by clinic. These logistic GEEs will be adjusted for P/C and patient features that may influence HPV vaccination series next step and completion, including age, sex, race/ethnicity, rurality, and HPV vaccination initiation status at study enrollment. Models comparing the Auto, Auto-Plus, and UC groups, will also include study arm. Comparisons between the study arms of the next-step and series-completion endpoints will be performed separately. For each endpoint, pairwise differences between arms will be assessed with a Bonferroni correction to achieve type I error control at 0.05, with p<0.017=0.05/3 needed for statistical significance. Predefined subgroup analyses will be performed by P/C and/or patient sex, age group, race/ethnicity, rurality, and HPV vaccination initiation status at study enrollment, and each of these characteristics will be assessed for effect moderation. Since next step completion and series completion will be captured via the EHR and the state-wide vaccine registry, we anticipate little missing data for these outcomes. Statistical Analysis and Power: Based on the **Table 2**, there are 1038 patients in the appropriate age range, of whom <50% will have completed the HPV vaccination series, for at least 519 patients within the eligible age range who have not yet completed the HPV vaccination series, with at least 173 in each study arm. 173 participants per study arm will ensure >80% power for detecting rate differences for both the next step endpoint and series completion endpoint exceeding 0.17, under the Bonferroni statistical significance benchmark of p<0.017. If the completion endpoint rate is 50% in the Auto-Plus arm and is 33% in the UC arm (rate difference 0.17), then the proposed study will have 80% power for detecting a difference by arm. Moderators: We will assess differences across study arms in our secondary outcome: missed opportunities, defined as patients who receive other recommended vaccinations, but not HPV. We will also explore possible moderators of effectiveness: age (11– 14, 15–17), ethnicity (Hispanic vs. non-Hispanic white), sex (male vs. female vs. other), language (Spanish vs. English), poverty status (<100% Federal Poverty Level vs ≥100% Federal Poverty Level), and insurance status (commercial vs. Medicaid vs. other). Thus, we will consider **sex a biological variable**, an important distinction because of differing rates of HPV vaccination and barriers faced by adolescent males and females. 132-135 By assessing differences in effectiveness across the life course of ages 11-14 and 15-17, we will understand differences in groups for whom 2 doses and 3 doses of the vaccine is recommended. Each potential moderator will be tested separately by considering its main effect and interaction with study arm in the logistic mixed effects models (Aim 2). Evidence of differential intervention effectiveness will be supported by an overall test of

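### The main models rest on a variance from four clinics, with no stated reference distribution, although participants are randomised individually within clinic; the strata also need one agreed list

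*Combined protocol and SAP*

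**What the plan says.** The opening of C.5 (Aim 2) sets the design: "We will implement and evaluate the intervention in 4 clinics using an individual-RCT design". C.5.b allocates caregivers individually in a 1:1:1 ratio. C.5.d (Study Design) does so "with separate randomizations within each clinic (Ocean Shores, Aberdeen, Elma, or Yelm) and patient-level HPV vaccination initiation status (series initiated or not initiated".

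C.5.d (Statistical Approaches) fits logistic GEE models to next-step receipt at 6 months and to series completion at 13 months, using "bias-reduced robust sandwich variance estimators 131 clustered by clinic". The models contain study arm and adjust for participant features "including age, sex, race/ethnicity, rurality, and HPV vaccination initiation status at study enrollment". Clinic is not named as a covariate, so its only stated role is as the cluster. Language is not named either. Each pairwise comparison must reach 0.017 (0.05/3). Sidedness, the GEE working correlation and the reference distribution are not stated. C.5.d (Statistical Analysis and Power) gives 173 per arm, at least 519 in all, and 80% power for 33% versus 50%.

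On strata, C.5.b says "We will select a cohort of approximately 1,038 P/C of patients from the 4 clinics", with randomisation "stratified by clinic, sex, and language preference (English, Spanish, other". It omits initiation status, and the Study Design paragraph of C.5.d omits sex and language.

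**The concern.** A sandwich variance clustered by clinic learns its precision from the clinics, not from the participants. With four clinics it has at most about three degrees of freedom. It has fewer in practice, because one clinic holds more than half the patients in Table 2 (Yelm, 566/1038 = 54.5%). The bias-reduced form corrects the average size of the variance but not its instability. The result then depends heavily on the reference distribution, which is left open.

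The design does not need this clustering to compare arms within these four clinics. All three arms occur in every clinic, so differences between clinics in baseline uptake fall out of the arm contrast. At stake are the significance threshold and the power of all three pairwise tests on both outcomes.

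The two lists of strata raise a separate and smaller question: which randomisation list is to be built.

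**Working it through.** **1. The plan's power.** Inputs from C.5.d: n = 173 per arm, rates 0.33 and 0.50, alpha 0.017 (two-sided assumed). The mean rate is 0.415.
- SE under the null = sqrt(2 x 0.415 x 0.585/173) = 0.0530
- SE under the alternative = sqrt((0.33 x 0.67 + 0.50 x 0.50)/173) = 0.0522
- Power = Phi[(0.17 - 2.387 x 0.0530)/0.0522] = Phi(0.83) = 79.8%

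The stated 80% therefore reproduces, under independent participants and a normal critical value.

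**2. Rough check on the reference.** The expected test statistic is about 0.17/0.0522 = 3.26. The two-sided 0.017 critical value is 2.39 for the normal, 4.82 for t on 3 df and 7.57 for t on 2 df. The planned effect clears only the first. Noncentral t gives power of about 30% on 3 df and 18% on 2 df.

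**3. Simulation.** The two main sets had N=519, blocked allocation or exact balance of arms within clinic, 4,000 runs per setting and UC at 33%. Auto-Plus was compared with UC. All other inputs are assumptions.
- Logistic model adjusted for age, sex and initiation status. Clinic sizes were 79/120/36/284 (pro rata to Table 2) or 98/121/26/274 (pro rata to an estimate of those not complete). The spread between clinics was none or taken from Table 2. Assumed: 30% initiated (OR 1.5), 13% Spanish preference (OR 1.4), sex OR 1.2.
- Linear-probability analogue without covariates. Clinic sizes were 79/120/36/283 and the clinic SD was 0 or 0.10 on the risk scale. The Satterthwaite df came to 1.92.

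Shorter linear-probability runs (1,200 per setting) gave similar results and are included in the ranges.

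| Variance and reference | True null rejected | Power, 33% vs 50% |
|---|---|---|
| Four-clinic sandwich, normal | 11-13% | about 79% (linear set, 4,000 runs), at that inflated error |
| Four-clinic sandwich, t(3) | 2-3% | 34-38% |
| Four-clinic sandwich, t(about 1.9) | under 1% | 11-13% |
| Clinic fixed effects, model-based or individual-level robust errors | 1-2% | 78-83% |

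With 4,000 runs the Monte Carlo SE is about 0.5 points at 12% and 0.8 points at 35%.

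**4. Clinic terms added, clustering kept.** Null rejection with a normal reference stays at 11.7-13.4% (logistic set), and the Satterthwaite df stays at 1.92 (linear set). The variance estimator is the problem, not the missing terms. In the logistic set without clustering, adding clinic and language terms raised power by only 0.2-1.7 points.

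**5. Strata.** Two sex levels are assumed, since C.5.b gives none.
- C.5.d: 4 x 2 = 8 cells; 519/8 = 65 per cell
- C.5.b: 4 x 2 x 3 = 24 cells; 519/24 = 22 per cell
- All crossed: 4 x 2 x 3 x 2 = 48 cells; 519/48 = 11 per cell

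At 1,038 each average doubles, to 130, 43 and 22.

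**The case against.** **The plan is unfinished, not wrong.** The covariate list is introduced as examples, so clinic could still be added. The working correlation is open, and C.4.a says the trial protocol will be finalised after the Bootcamp stage. This stands as far as it goes. But step 4 shows that adding clinic terms does not help while the clustering stays, and a working correlation would still use clinic only as the cluster.

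**The 11-13% belongs to a reference the plan never states.** This stands. A small-cluster reference could be chosen and would bring the error near or below the threshold. It would do so at 11-38% power, against the 80% claimed.

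**The simulated models are not the planned one.** They omit race/ethnicity and rurality, and the eligible clinic sizes are assumed. This stands. The pattern nevertheless held with and without clinic differences and in both forms of model.

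**Clinic fixed effects are not valid for every purpose.** Clinic teams deliver the intervention, so its effect may differ between clinics. With fixed effects, model-based errors and an arm effect averaging zero, null rejection was 1.5% when the between-clinic SD of the arm log-odds ratio was 0. It was 4.0% at SD 0.2, about 6% at 0.3 (5.7% and 6.5% in two runs) and 10.2% at 0.4. These SDs are assumed. The limitation stands and should be written into the plan.

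**The two strata statements may describe one crossed scheme.** They may, and no text rules it out. Sex and initiation status are in the model either way, so chance imbalance in them is adjusted for under either scheme.

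**Conclusion.** The concern holds for the variance. Under each of the three references examined, the planned test either exceeds 0.017 or falls far short of 80% power. The exact percentages are illustrative. They rest on N=519, assumed eligible clinic sizes, two-sided tests and simplified covariates.

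Three stronger readings are tempting, and the documents do not support them:
- That the trial's type I error is about 12%. That needs a normal reference, which the plan does not state.
- That the sample-size arithmetic is wrong. It reproduces; it simply does not describe the planned analysis.
- That C.5.b and C.5.d contradict each other on strata, or that C.5.b applies only to patients not yet initiated. The lists can be crossed. C.5.b does begin from initiation, where "Sea Mar analysts will create a real-time list of patients due for an initial HPV vaccine dose", but it applies its strata to the whole cohort. What is missing is a statement of the scheme. The list cannot be built or audited without it, but on its own this has little effect on the results.

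**What to change.** **Variance.** In both the primary and secondary models, replace the clinic-clustered sandwich with clinic fixed effects and model-based or individual-level robust errors. Keep the covariates already named, and add any other factor used to stratify (language, if it is used). State the reference distribution and that the tests are two-sided. State also that inference is to these four clinics or assumes a common arm effect.

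**Strata.** Give one list in both C.5.b and C.5.d, for example clinic by initiation status, or say explicitly that all factors are crossed. If sex is a stratum, say whose sex and how many levels.

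**Cost.** Wording in two sections, three clinic terms, and language terms if language is a stratum. Preferred language is already among the variables C.5.b plans for the registry. Two prices are paid. The conclusion does not extend to other clinics without the common-effect assumption. And rurality, if coded by clinic as in Table 2 (40.1% at three clinics, 29.0% at Yelm), is aliased with clinic, so it must be coded per patient or dropped.

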- Interactive web-based coaching tool: Live calls will be facilitated by an interactive web-based coaching tool that prompts patient navigators during live phone calls with P/C on how to best respond to varying types and levels of P/C vaccine hesitancy. This tool will be developed by Drs. [name] and [name] in partnership with HCl's bioinformatics core. P/C identified vaccine hesitancy barriers may fall within the broad domains related to vaccine confidence, vaccine complacency, and vaccine convenience (Figure 2).
- Patient navigators: trained staff who promote healthful behaviors by addressing barriers to care. Navigators can respond to the cultural needs of their patients—such as values of *personalismo* or *respeto*. 127, 128

**C.5.c.** Intervention Process: Focused on HPV vaccine series completion. The BCT process will define the format (mode and frequency) and content of messages to promote vaccine series completion. The clinic-level analysts will generate real-time lists of patients who have initiated the HPV vaccine and are due for a follow-up dose, stratified by age group (11–14 vs. 15–17). The list will include adolescents age 11–14 years who have completed an initial dose of the HPV vaccine and are due for a second dose (within 6-12 months) and those aged 15–17 who are due for a second or third dose. While Auto and Auto-Plus interventions for series

completion may use some of the same components as vaccine initiation (automated calls, live calls, text messages, emails, and mailings), some notable differences will likely exist. HPV vaccine initiation may bundle recommendations for HPV and for other needed vaccines (e.g., "[Patient name] is due for the following vaccines: HPV; meningococcal; Tetanus, Diphtheria, Pertussis"), whereas series completion will not need bundled messages. Series completion reminders will include scheduling and appointment reminders.

**C.5.d. Evaluation:** Based on our previous research and conversation with clinic staff, we have designed Phase I to include multiple components. Using the Proctor Implementation and RE-AIM frameworks, we will track intervention reach and effectiveness. We will conduct one-on-one interviews with participants and debrief interviews with HCP to illuminate persistent barriers to HPV vaccination uptake and factors important to program acceptability, maintenance, and sustainability. **Table 3** summarizes these measures.

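### Reach for series completion is read at 6 months but the outcome at 13, so completion outreach to 11–14-year-olds who start after randomization falls largely or wholly outside the reach window

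*Combined protocol and SAP*

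**What the plan says.** All references are to the combined protocol and SAP.

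- **Section C.5** names two quantitative measures for Aim 2: "Our quantitative evaluation will assess intervention effectiveness and reach".
- **Table 3, reach.** The row "Reach of RCT – secondary outcome (completion of HPV vaccine series" is timed at 6 months. Its formula is "N part. receive program/ N anticipated, reasons". Neither the program nor the anticipated number is defined.
- **Table 3, effectiveness.** The row "Effectiveness of RCT – secondary outcome" is timed at 13 months. For the primary outcome, both the reach row and the effectiveness row are at 6 months.
- **Section C.5.d, Study Design,** compares "completing the HPV vaccination series at 13 months between Auto, Auto-Plus, and UC arms" and gives a "total participant time on study of 13 months".
- **Section C.5.c** has completion outreach run from "real-time lists of patients who have initiated the HPV vaccine and are due for a follow-up dose". Children aged 11–14 on that list "are due for a second dose (within 6-12 months"; for ages 15–17 no interval is given.
- **Who is randomized.** C.5.b draws the randomized list from patients due for a first dose. Study Design randomizes all who have not completed the series, stratified by whether they have started it.

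**The concern.** The completion pair is the only one in Table 3 where reach and effectiveness have different time points, and no reason is given. The gap is more than a label because of how completion outreach is triggered. By the plan's own interval, a child aged 11–14 whose first dose follows randomization joins the completion list in month 6 or later. Most or all of that family's completion outreach then falls in months 6–13, which the reach row does not count.

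The stake is interpretation. If completion at 13 months shows little difference between arms, the natural next question is whether the completion outreach was delivered. A reach figure that stops at month 6 cannot answer that for a large group of participants, and it could suggest poor delivery where there was none.

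**Working it through.** **1. The plan's own figure.** The plan states no reach figure. Its only design calculation is 80% power for 50% against 33% with 173 per arm at 0.05/3 (two-sided assumed, z = 2.394).
- Pooled standard error: √(2 × 0.415 × 0.585 / 173) = 0.0530. Unpooled: √((0.33 × 0.67 + 0.50 × 0.50) / 173) = 0.0522.
- Power = Φ((0.17 − 2.394 × 0.0530) / 0.0522) = 79.6%, or 80.6% with the unpooled error throughout.

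The stated 80% reproduces. Reach does not enter this calculation.

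**2. Earliest due time.** For ages 11–14 not started at randomization, the first dose comes at month t ≥ 0, so the second is due at t + 6 ≥ 6. To come due by month 13 the first dose must come by month 7. Children aged 11–14 already started at randomization have all passed the 6-month minimum by month 6.

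**3. Size of the affected group.** Inputs are the Table 2 clinic sizes (158, 241, 73, 566; total 1038) and the initiation and completion rates by age band. Not started = 100 − initiated %. Started but not complete = initiated % − completed %. The documents do not give the age mix, so I assume ages 11–12 are 2/7 of ages 11–17 (range 20–40%) and ages 13–14 are 2/5 of ages 13–17.

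At the base mix, summed over clinics:

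| | Not started | Started, not complete |
|---|---|---|
| Ages 11–12 | 159.5 | 97.2 |
| Ages 13–17 | 307.7 | 113.3 |

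The total is 677.7 non-completers.
- Not started, 11–14: (159.5 + 0.4 × 307.7) / 677.7 = 282.6 / 677.7 = **41.7%** (38–46% over the range)
- Not started, 15–17: 0.6 × 307.7 / 677.7 = 27.2%
- Started, 11–14: (97.2 + 0.4 × 113.3) / 677.7 = 21.0%
- Started, 15–17: 0.6 × 113.3 / 677.7 = 10.0%

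**4. Reach with a whole-cohort denominator.** Assume one third of the not-started begin the series, equally across ages and early enough to come due by month 13.
- Highest possible by month 6: 31.1% (already started), plus between 0 and 27.2% / 3 = 9.1% (newly started 15–17, for whom no interval is given) = **31–40%**.
- Highest possible by month 13: 31.1% + 9.1% + 41.7% / 3 = **54%**.

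**5. Reach with a denominator of those due by month 6.** The time point then causes no shortfall, but months 6–13 are not covered.

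**6. Share of eventual recipients who are certainly late** (newly started 11–14 divided by everyone ever due).
- All non-completers randomized (Study Design), 20% of the not-started beginning: 0.2 × 41.7 / (31.1 + 0.2 × 68.9) = 19%. All beginning: 41.7 / 100 = 42%. Over the age range: 17–46%.
- First-dose list only (C.5.b): 41.7 / (41.7 + 27.2) = 60%, or 55–68% over the age range.

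**The case against.** **The figure need not be low.** The reach denominator is undefined. If it counts participants due by the reading date, the 6-month value is not biased low. This stands, so a reader should not infer that reach is understated by construction. The whole-cohort reading is still plausible: the effectiveness rows use the same denominator term, and C.5.d defines effectiveness over eligible children. On the narrower reading the figure still stops short of the 13-month outcome.

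**Most reminders need not be late.** A reader might infer that most completion reminders come after month 6. Under Study Design, those already started can be listed from entry, and the certainly late share is 17–46%. A majority needs the first-dose-list reading in C.5.b (55–68%). Otherwise every newly started 15–17-year-old must be late too, with about 45% or more of the uninitiated starting. It is also tempting to cite all uninitiated children, about 69% of non-completers, but the interval argument covers only ages 11–14.

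**Reminders might precede the due date.** C.5.c mentions scheduling reminders and C.4.b mentions prompting on time, while timing is left to Bootcamp Translation. This stands in part: a family that starts soon after randomization might be contacted shortly before month 6. Hence largely or wholly outside the window, not zero reach.

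**The program might mean all outreach in the arm.** Both reach rows share one formula. But on that reading two rows at the same time point would give the same number, so a separate completion row would add nothing.

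**Other data cover the gap.** The row records reasons, the registry logs dated contacts, and fidelity is measured in Year 3. This softens the harm, but none of it is specified as reach over the 13-month window.

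**Conclusion.** The point holds as a mismatch of time points with a traceable consequence. As written, Table 3 leaves most or all completion outreach to newly started 11–14-year-olds out of the completion reach figure. That group is drawn from about 42% of non-completers (38–46%). The direction of error depends on the denominator. With the whole cohort, reach is understated, illustrated by 31–40% at most by month 6 against 54% by month 13. With only those due by month 6, reach is incomplete rather than biased.

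These sizes rest on the Table 2 rates, the assumed age mix, the assumed one-third start rate, and the plan's own 6-month minimum for ages 11–14. The documents do not support a claim that overall reach would be near zero, since children already started can be reached from entry.

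This is a minor point. Reach is descriptive, and neither the effectiveness comparisons nor the power depends on it. It is still worth correcting, because reach is one of Aim 2's two named quantitative measures and would be read beside the 13-month result.

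**What to change.** 1. In Table 3, change the time point of the secondary-outcome reach row from 6 to 13 months. The 6-month value can stay as an interim reading.
2. Define the denominator of that row as randomized intervention-arm participants who became due for a follow-up dose by month 13, and state that the program means completion outreach.
3. Reconcile C.5.b (patients due for a first dose) with Study Design (all non-completers) on who is randomized, because the size of the affected group depends on it.

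The cost is one table cell, one definition and one clarification. Section C.5.b already plans dated reports of intervention activity, and participants are on study for 13 months, so no new data source appears necessary. The sponsor should confirm that contact logs are kept for the full 13 months, which the documents do not state.
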